11.7.5 Pooling of Investigative Sites

Not applicable.

11.7.6 Safety Analysis

Safety evaluations include vital signs, AEs and concomitant medications.

The safety profile will be assessed in terms of overall AEs, vital signs findings, and concomitant medication usage over the 10-day treatment period, as well as at the 4 weeks follow-up period after treatment.

Vital signs will be summarized descriptively. Change from baseline will also be summarized.

Prior and concomitant medications will be coded using the World Health Organization (WHO) Drug dictionary. Medications initiated prior to start of study medication and maintained during

the study, or taken during the course of the trial will be considered as concomitant medications. Concomitant medications will be summarized according to the preferred terms.

Adverse events will be coded using the Medical Dictionary for Regulatory Activities (MedDRA). The number and percentage of subjects who experienced any AE as well as serious AE will be presented by system organ class and by preferred term within system organ class. All AEs will be similarly presented by seriousness criteria and by relationship to Pylera® (related/not related).

Safety analysis will be performed on the safety population for all subjects and for treatment successes and failures separately. No statistical comparisons will be performed.

There will be an additional follow-up for neurological adverse events indicative of encephalopathy through a separate and concomitant safety program, i.e. the Intensive Monitoring Program, as part of Risk management plan of Pylera®. A “Pharmacovigilance reporting form – for neurological events with bismuth” shall be completed for each case where neurological symptoms listed in the Appendix 3, accompanied or not by bismuth whole blood concentration above 50 µg/L occur. There will be a case review and confirmation by the Scientific Committee of the Intensive Monitoring Program for the diagnosis of encephalopathy. The assessment of the correlation between bismuth concentration and occurrence of neurological symptoms will be provided in the Periodic Safety Update Reports (PSUR) and in the reports from the Intensive Monitoring Program.

11.7.7 Pharmacokinetic / Pharmacodynamic Analysis

This study will focus on the detection and assessment of bismuth concentrations within the circulating plasma and whole blood compartment.

The initiation of any encephalopathy by an external compound requires the absorption of the material(s) and its transport to the central nervous system and its eventual crossing of the blood-brain-barrier; material which is not absorbed and eventually excreted in the feces will have no potential to induce an encephalopathy.

It is not known which metabolite(s) (if any) bismuth subcitrate potassium transforms to following ingestion of Pylera® by patients, and how such metabolites are further transformed. In the context of the clinical cases reported in the 1970s, it was never confirmed which bismuth metabolites generated the bismuth-associated encephalopathies.

One metabolite – trimethylbismuth (TMB) – is produced by methanoarchaea bacteria^{31,32,33} present within the intestinal flora and is detectable at picogram levels within the circulating plasma compartment and by examination of respiratory exhalation³⁴. TMB has been implicated in

bismuth-associated encephalopathies following the demonstration of encephalopathies in experimental animals exposed by inhalation to large uncontrolled quantities of TMB³⁵.

The detection of total bismuth (metal) rather than individual bismuth metabolites permits the detection of all bismuth circulating within the bloodstream irrespective of whatever metabolite form the bismuth atom is found in. Whole blood TMB will be evaluated using an analytical method derived from Boertz *et al.* (2009)³⁴ due to the possibility of encephalopathy arising from animal models. Post-treatment plasma and whole blood concentrations of bismuth (metal and TMB) will be described after subtraction of the baseline value for each subject using the following formula:

$$\text{Accumulation Value} = (\text{EOT bismuth concentration} - \text{Day 0 bismuth concentration})$$

This comparison will include an evaluation of bismuth concentration in subjects who report neurological AEs and subjects who do not report neurological AEs.

After comparison on the whole sample, data will be stratified by the PPI used in combination with Pylera® and the comparison will be repeated in strata where sample size allows.

An additional comparison will be made of all post-treatment concentrations in the omeprazole group versus post-treatment concentrations of all other PPIs pooled together. For each subject the C_{\min} will be grossly estimated assuming an elimination half-life of 19.95 hours³⁰ by the equation:

$$C_{\min} = \frac{C_{\text{observed}}}{e(-0.0347 * t)}$$

where t is the time elapsed between last dose intake and sampling time.

Individual observed results will also be classified as “above” or “below” the Hillemand *et al.*²⁷ alert threshold of 50 µg/L²⁷ for total whole blood bismuth concentrations solely as TMB has been calculated by Aptalis Pharma US, Inc. to exist at approximately 1:10,000 the level of average circulating bismuth concentrations.

For subjects who are already below 50 µg/L on Day 11, no other action will be performed and such subjects will be considered to have reached safe whole-blood levels within an acceptable time.

For subjects who are above 50 µg/L, the time required to reach 50 µg/L will be grossly estimated, again assuming an elimination half-life of 19.95 hours by the equation:

$$T_{recov} = \frac{\ln\left(\frac{50}{C_{min}}\right)}{-0.0347}$$

Such subjects will also be referred for evaluation and potential inclusion in the separate Intensive Monitoring Program.

The number of subjects requiring more than 24 hours to reach safe levels and the time required will be considered to draw conclusion on the clinical safety of Pylera® with regard to bismuth toxicity.

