3 STUDY DESCRIPTION (STUDY DESIGN)

3.1 OVERALL STUDY DESCRIPTION

This study is a multicenter, open-label, single-arm, clinical trial to be conducted exclusively in France and involving two hundred (200) eligible subjects. A detailed description of study procedures and study conduct is presented in Section 9 and Appendix 1 of this protocol.

The study will consist of an Investigator pre-selection period, and a subject treatment period.

The Investigator pre-selection period will identify likely prescriber profiles within a national reimbursement database (e.g., the EGB representative sample in France), or other applicable databases to determine the distribution of Gastroenterologists (GE) and General Practitioners (GP) based on appropriate measures including but not limited to the prescription of UBT or other diagnostic tests for *H. pylori*, or the prescription patterns of Pylera® when it is marketed.

[figure not shown]
This pre-selection analysis will also identify usage patterns per prescriber in order to evaluate the number of prescribers required to accrue the expected number of subjects without seeding.

Following identification of the GE/GP ratio and the calculation of sites required to complete recruitment within the 24 month timeframe, specific databases of health professionals such as CEGEDIM will be used to contact GPs and/or GEs to propose participation in the study as per the GE/GP prescriber ratio described above.

The subject study period will be conducted at these participating sites and will be comprised of three steps as follows:

1. Inclusion Visit (Day 0)
2. End of Treatment Period (EOT) Visit (Day 11)
3. End of Study (EOS) Visit (Day 39)

An allowance for participation will be provided to each patient at the end of the 3rd visit.

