9.2.1 Subjects who completed treatment with Pylera®

Subjects who have completed the 10-day treatment with Pylera® will return to complete the following procedures as part of the EOT Visit:

- Vital signs measurement (blood pressure, pulse rate)
- Recording Pylera® treatment description and compliance
- Recording of concomitant medications
- Recording of AEs

The presence of CNS adverse events of specific interest as listed in Appendix 3 will be assessed at this visit with the specific form “Pharmacovigilance reporting form-neurological disorders and bismuth” developed for the collection of the adverse events of special interest as part of the Intensive Monitoring Program that will be completed by the Investigator.

Subjects will provide one blood sample as the post-treatment sample (D11 sample) for assessment of plasma and whole blood bismuth concentrations as well as whole blood TMB concentrations as per the procedures outlined in Appendix 2.

Subjects who demonstrate bismuth accumulation in whole blood at the EOT Visit ($> 50 \mu\text{g/L}$) will be requested to return immediately to the laboratory to draw a third blood sample for evaluation of bismuth. If bismuth concentration remains sustained and subject interview with Investigator confirms that no third-party source of bismuth was consumed outside of the context

of this study, the subject will be referred to the separate Intensive Monitoring Program to be evaluated for inclusion.

Subjects will return 28 days after the EOT Visit to complete the EOS Visit. At this visit, subjects will complete:

- Vital signs measurement (blood pressure, pulse rate)
- Recording eradication test
- Recording of concomitant medications
- Recording of AEs

The presence of CNS adverse events of specific interest as listed in Appendix 3 will be assessed at this visit with the specific form “Pharmacovigilance reporting form-neurological disorders and bismuth” developed for the collection of the adverse events of special interest as part of the Intensive Monitoring Program that will be completed by the Investigator.

Subjects who demonstrate a positive diagnostic *H. pylori* test (breath test, biopsy, or other test at the discretion of the Investigator) at End of Study will be documented by the completion of a specific form entitled “Targeted follow-up form – Pylera® eradication therapy failure”. These subjects will be referred to treatment for *H. pylori* infection outside of the context of this study.

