10 ADVERSE EVENTS

Subjects receiving any investigational drug require careful observation. Any adverse event/concurrent illness experienced by a subject during any portion of the study must be described in detail and be fully evaluated by the Investigator. The Investigator is responsible for recording all adverse events observed or reported during the study from Inform Consent signature until date of completion/discontinuation, regardless of the drug-related assessment and/or clinical significance. Any pertinent information must be recorded in the CRF and additional comments describing the course and outcome of these events should be provided as appropriate.

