10.4.1 Assessment and Recording

An AE, whether or not considered causally related to the treatment, must be promptly documented and recorded. At each study visit, after the subject has had an opportunity to spontaneously mention any problems, the Investigator should inquire about AEs by asking the appropriate open questions. In addition to straightforward subject observation (e.g., headache, nausea, etc.), AEs will also be documented from any data collected in the CRF (e.g., laboratory values, physical examination findings, etc.) or other documents (e.g., subject diaries) that are relevant to subject safety.

At each follow-up visit or assessment by phone or otherwise, all AEs, whether observed by the Investigator or one of his or her professional collaborators, or reported by the subject

spontaneously or in response to an open question, will be recorded in the Adverse Event Form included in the CRF with the following information.

- **Name of the AE:** Name should be a medical term. When possible, the Investigator should differentiate an illness entity from isolated symptoms or signs. For instance, the term “flu” should be recorded instead of listing all the flu-related symptoms. Where a differentiation is not possible, symptoms and signs should be separately recorded and evaluated as **Adverse Events**.
- **Start date and stop date (or statement that the event is continuing) of the AE**
- **Imputability of Pylera®:** evaluate the causal relationship between Pylera® and the AE as described in section 10.4.2
- **Seriousness criteria** as defined in section 10.1

The Aptalis Pharma US, Inc CRA who visits the center will check the completeness and accuracy of the Adverse Events Form. Wherever possible, all AEs regardless of the seriousness must be followed through resolution.

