APPENDIX 3 – CENTRAL NERVOUS SYSTEM ADVERSE EVENTS OF INTEREST

Bismuth neurotoxicity is typically characterized by encephalopathy, which is defined as any degenerative or diffuse disease of the brain that alters brain structure or function.

In order to select the appropriate terms, the original Standardized MedDRA Query (MedDRA 15.1SMQ Noninfectious encephalopathy/delirium (20000133)) was revised to specifically address the bismuth encephalopathy and include signs and symptoms that are specific to this risk.

Preferred Terms (narrow scope): Encephalopathy, Toxic encephalopathy

Preferred Terms (broad scope):

Abnormal behavior;	apraxia; Gait disturbance;	changes; Mood altered;
Agitation; Agraphia; Alexia;	Generalised non-convulsive	Myoclonus; Paresis anal
Altered state of	epilepsy; Grand mal	sphincter; Partial seizures;
consciousness; Amnesia;	convulsion; Hallucination;	Partial seizures with
Anal sphincter atony;	Hallucination, auditory;	secondary generalization;
Apathy; Ataxia; Bladder	Hallucination, gustatory;	Personality change;
sphincter atony; Cerebellar	Hallucination, olfactory;	Personality disorder;
ataxia; Cerebellar syndrome;	Hallucination, synaesthetic;	Psychomotor seizures;
Clonic convulsion; Coma;	Hallucination, tactile;	Restlessness; Simple partial
Coma scale abnormal;	Hallucination, visual;	seizures; Sleep disorder;
Complex partial seizures;	Hallucinations, mixed;	Slow response to stimuli;
Confusional state;	Hypersomnia;	Sluggishness; Somnolence;
Convulsion; Convulsions	Hyporesponsive to stimuli;	Speech disorder; Stupor;
local; Coordination abnormal;	Illogical thinking	Thinking abnormal; Tonic
Delirium; Depressed level of	Incontinence ; Judgement	convulsion; Tremor;
consciousness; Disturbance in	impaired; Lethargy; Listless;	Unresponsive to stimuli;
attention; Dysarthria;	Loss of consciousness;	Urinary incontinence.
Dysgraphia; Dyspraxia;	Memory impairment; Mental	
Faecal incontinence; Gait	impairment; Mental status	

A “narrow” scope represents the condition of interest and a “broad” scope helps to identify all possible cases, including some that may prove to be of little or no interest on closer inspection. Thus, a “narrow” search yields “specificity” while the “broad” search yields “sensitivity.”

The presence of these events will be identified and assessed at the End of Treatment and End of Study visits only as the event would need to be treatment-emergent in order to be potentially associated with potential bismuth neurotoxicity.

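### The bismuth comparison by neurological AE status does not separate events recorded at the End of Treatment visit from events first recorded later, when the investigator may know who exceeded 50 µg/L

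*Protocol*

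**What the plan says.** **The comparison.** Section 11.7.7 describes EOT bismuth minus Day 0 bismuth and adds: "This comparison will include an evaluation of bismuth concentration in subjects who report neurological AEs and subjects who do not report neurological AEs". It sets no limit on when a qualifying event must have been recorded.

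**When events are collected.** Section 10 has the investigator record AEs "from Inform Consent signature until date of completion/discontinuation, regardless of the drug-related assessment", so collection continues to the EOS visit at about Day 39. Appendix 3 says that the CNS events of interest are "identified and assessed at the End of Treatment and End of Study visits only". Section 9.2.1 applies the same investigator-completed form at both visits: "The presence of CNS adverse events of specific interest as listed in Appendix 3 will be assessed at this visit with the specific form".

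**What a high result triggers.** Under the Study Synopsis and sections 3.2 and 9.2.1, a whole blood result above 50 µg/L at EOT leads to immediate recall for a third sample. If the level persists and "subject interview with Investigator confirms that no third-party source of bismuth was consumed" outside the study, the subject is referred to the Intensive Monitoring Program for evaluation. Section 11.7.7 plans no further action for subjects below 50 µg/L.

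**Blinding.** Section 3.1: "This study is a multicenter, open-label, single-arm, clinical trial to be conducted exclusively in France". Nothing in the protocol keeps the EOS assessor unaware of the Day 11 result.

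**The concern.** A comparison of exposure between subjects with and without an event is fair only if recording of the event does not depend on the exposure result. Here it may, for part of the data. The EOT form is completed at the visit where the Day 11 sample is drawn. The EOS form is completed 28 days later by an investigator who may by then have been told that a particular subject was above the alert value.

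The Appendix 3 broad list includes terms such as sleep disorder, somnolence, restlessness, lethargy and altered mood, where recording depends on how closely one asks. Appendix 3 itself accepts that broad terms may catch cases of little or no interest.

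Flagged subjects are by definition those with the extreme concentrations, so moving even one into the AE group has leverage on a mean. The likely error is a false signal. That matters because bismuth neurotoxicity is the concern that led regulators to request the study (sections 1.1 and 1.2).

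**Working it through.** The protocol gives no figure for this comparison, so there is nothing to reproduce. The check is of the sequence of events and then of possible size.

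**1. Sequence**
- Day 11: CNS form completed and sample drawn. Samples are frozen and sent to a central laboratory (Appendix 2), so the form normally precedes the result.
- Day 11 to Day 39: result above 50 µg/L leads to recall, possible interview and referral. For a completer without symptoms who is below 50 µg/L, nothing further is planned.
- Day 39: same form, same investigator, result possibly known.

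Only events first recorded after the result are exposed to the problem.

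**2. Inputs**
- From the protocol: N = 200; typical level L = 4.66 µg/L (Phase I average 24-hour plasma trough, section 1.1).
- Assumed: k flagged subjects (0 to 10) at level H (60 µg/L; 80 µg/L as the upper case in step 3); true event rate p (2 to 10%), unrelated to bismuth; recording m times as likely in flagged subjects (m = 1 to 3).

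**3. One flagged subject certainly reclassified** (20 subjects with an AE, 180 without, all others at 4.66 µg/L)

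| | H = 60 | H = 80 |
|---|---|---|
| Non-AE mean before | (179 × 4.66 + 60)/180 = 4.97 | (179 × 4.66 + 80)/180 = 5.08 |
| Difference before (AE minus non-AE) | 4.66 − 4.97 = −0.31 | 4.66 − 5.08 = −0.42 |
| AE mean after | (20 × 4.66 + 60)/21 = 7.30 | (20 × 4.66 + 80)/21 = 8.25 |
| Difference after | 7.30 − 4.66 = +2.64 | 8.25 − 4.66 = +3.59 |

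All values are in µg/L.

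**4. Expected difference with no true association**

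A = kmp + (N − k)p

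AE mean = [kmpH + (N − k)pL]/A

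Non-AE mean = [k(1 − mp)H + (N − k)(1 − p)L]/(N − A)

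Example with k = 1, p = 0.10, m = 2, H = 60:
- A = 0.2 + 19.9 = 20.1
- AE mean = (12 + 92.73)/20.1 = 5.21
- Non-AE mean = (48 + 834.61)/179.9 = 4.91
- Difference = 0.30 µg/L

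Over p = 2 to 10%, at H = 60:

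| k | m = 1 | m = 2 | m = 3 |
|---|---|---|---|
| 0 | 0 | 0 | 0 |
| 1 | 0 | 0.28 to 0.30 | 0.56 to 0.61 |
| 5 | 0 | 1.34 to 1.47 | 2.62 to 2.87 |
| 10 | 0 | 2.56 to 2.80 | 4.89 to 5.37 |

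As an odds ratio for a recorded AE, above versus below 50 µg/L, m = 2 gives (0.04/0.96)/(0.02/0.98) = 2.04 at p = 2% and (0.20/0.80)/(0.10/0.90) = 2.25 at p = 10%. At m = 1, which is what restriction to events recorded before the result achieves, the expected difference is 0 and the odds ratio is 1.

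Step 3 is far larger than the k = 1 row because it takes the reclassification as having happened. Step 4 averages over whether it happens.

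**The case against.** Much can be said for the plan as it stands.

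- **Extra contact is not confined to high bismuth.** A reader might infer that only subjects above 50 µg/L are seen again. Section 3.2 and Appendix 2 also recall subjects with neurological symptoms, whatever their level, and section 9.2.2 gives early discontinuers a safety call. This objection stands. Symptomatic subjects are already in the AE group, however, so the asymmetry remains among completers without symptoms at Day 11, who are the ones that can be reclassified.
- **The recall is not a CNS assessment.** It is a laboratory visit, and the conditional interview concerns other sources of bismuth. Section 10.4.1 covers events "At each follow-up visit or assessment by phone or otherwise, all AEs", but that does not make every contact a neurological enquiry. This stands: the stronger route is the investigator's knowledge at EOS.
- **All completers get the same form at the same two visits.** True, and it limits the problem to later events. A common form does not remove the influence of knowing the result when subjective symptoms are judged.
- **Knowledge at EOS is not established.** No assay turnaround is fixed, and fast processing is stated only for a neurological AE at Day 11. This stands. Immediate recall makes earlier knowledge plausible, not certain.
- **Few or no subjects may be flagged.** Phase I saw no sustained levels above about 20 µg/L, and blood peaks above 50 µg/L, in 8 of 28 subjects, lasted under an hour. This stands and makes zero bias quite possible.
- **Consequences are limited.** The analysis is descriptive, medians are planned too (section 11.7.2) and one subject barely moves a median. The protocol's safety conclusion rests on time to fall below 50 µg/L, and encephalopathy cases are reviewed by a committee. All true, but describing a comparison does not make it unbiased.

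An analysis plan not shown here could add a time split. Section 11.7.7 as written groups subjects without one.

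**Conclusion.** The point holds in a limited form. The section 11.7.7 comparison mixes events recorded without knowledge of the result with events that may have been recorded with it. Any resulting distortion runs towards an association.

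The size depends on facts the protocol cannot supply in advance. It is zero with no subject above 50 µg/L or with results arriving after EOS. It is about 0.3 µg/L in expectation with one flagged subject at 60 µg/L and doubled recording. The AE-group mean reaches 7.3 to 8.25 µg/L if one subject at 60 to 80 µg/L is in fact reclassified into a group of 20.

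A reader might take the last figure, up to 77% above 4.66 µg/L (8.25/4.66 = 1.77), as the expected bias. The documents do not support that: it assumes certain reclassification and a high level. The 4.66 µg/L is also a plasma trough, standing in for baseline-subtracted values and set beside a whole blood flag. I take neurological AEs in section 11.7.7 to include the Appendix 3 broad terms.

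**What to change.** In section 11.7.7, present the comparison for neurological AEs recorded up to and on the EOT CNS form, labelled as the one made without knowledge of the Day 11 result. Beside it, show events first recorded after EOT, split by whether the subject had been recalled for exceeding 50 µg/L. Keep recall for symptoms distinct from recall for a high result.

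Classify by visit form and recall status. The protocol does not list an AE recording date (section 10.4.1 has start and stop dates) or a result release date (section 11.5.1 has sampling times), so the split should not rely on them.

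All events stay in the safety tables and clinical follow-up is unchanged. The cost is a change of analysis wording and one further display. The downside is fewer events in the EOT comparison. Later-onset events, which the four-week follow-up is meant to capture, are read from the adjacent display and must stay visible there.

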Although absorption of bismuth subcitrate potassium (the bismuth salt found in Pylera®) was found to be negligible during the product's development cycle^{24,25}, a Phase I study was conducted in *H. pylori*-infected subjects to document blood plasma and whole blood bismuth bioavailability under the full mode administration of Pylera® (10-day treatment period with medication intake with food). This study enrolled 32 subjects, well above the 24 subject minimum requested to account for the high variability of bismuth concentrations between subjects. The PK profile of bismuth in blood and plasma following 10-day QID dosing of Pylera® with omeprazole BID did not raise safety concerns regarding any risk of central neurotoxicity related to bismuth up to 28 days post-final dose²⁶.

Plasma and blood bismuth concentrations were similar, with steady state concentrations (SSC) attained by Day 4. All subjects had Day 10 average SSC below the Hillemand *et al.* (1977)²⁷ alert value of 50 µg/L bismuth. The chronic bismuth concentrations published by Hillemand *et al.* are generally accepted safety levels for which a physician must be alert to the possibility of encephalopathies (“alert value”: >50 µg/L sustained bismuth concentration) and to which a physician must act (“panic value”: >100 µg/L sustained bismuth concentration). Based on this proposal, sustained steady-state blood levels of bismuth lower than 50 µg/L should not be associated with severe (intensity) bismuth-related Adverse Events.

The complete population view of bismuth from this PK study showed high variability of bismuth concentration among the different subjects and samples. Nevertheless, certain trends were apparent. Samples from Days 1-9 (hours 0 → 208), drawn towards the end of the dosing interval of the first dosage of the day, reflected a low level of bismuth as the peak absorption levels which were not reflected in the sampling scheme. The average 24-hour trough plasma level (4.66 µg/L) reflected rapid distribution, and there were no sustained levels with any subject at any time above approximately 20 µg/L.

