9.1.2 Observations and Measurements

Following the granting of Informed Consent, each subject will be assigned a subject number in sequential order.

The following Inclusion Visit procedures and evaluations in addition to procedures normally conducted as part of standard of care will be performed after Informed Consent will be recorded in the appropriate sections of the CRF:

- Demographic data
- Confirmation of inclusion and exclusion criteria
- Date of Pylera® prescription
- Name of prescribed PPI
- Vital signs measurement (blood pressure, pulse rate), height and weight
- Disease history regarding *H. pylori* infection with previous *H. pylori* treatment and diagnostic tests with date and results (negative/positive)
- Co-morbidities, medical/surgical history
- Recording of prior and concomitant medications

Subjects will provide one blood sample as the baseline sample (D0 sample) for assessment of plasma and whole blood bismuth concentrations and whole blood trimethylbismuth (TMB) concentrations as per the procedures outlined in Appendix 2.

Once the D0 sampling is complete, subjects will be given an appointment for the second blood sampling (D11 sample) and subjects may initiate treatment with Pylera®.

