APPENDIX 2 – PHARMACOKINETICS BLOOD SAMPLING

The procedures described in this appendix detail the requirements for blood sampling and handling for pharmacokinetics samples.

Collection, processing, and transport will all be conducted with the samples shielded from light to minimize photo-degradation of any potential light-sensitive bismuth metabolite(s) within the samples.

1) Quantity collected and timeframe:

The total volume of blood drawn for bismuth and trimethylbismuth (TMB) pharmacokinetic assessment is anticipated to be 56 mL (8 x 7 mL tubes) over the full study period for each subject.

Blood samples will be drawn at two (2) timepoints in the study – one blood draw (amounting to 4 tubes, 7 ml each) will be done prior to the start of treatment with Pylera® plus PPI (presumed to be omeprazole) (Inclusion Visit), and a second blood draw sample (amounting to 4 tubes, 7 ml each) the day after the end of treatment with Pylera® plus PPI (EOT Visit). The date and time of the two blood samplings will be recorded and reported for each subject. The collection tubes will be shielded from light to minimize photo-degradation and frozen at -20°C before transport for measurement of bismuth and TMB concentration.

2) Type of tubes

Blood samples will be obtained from an antecubital vein using two types of tubes:

- For bismuth plasma concentration determination: coded EDTA K2 Vacutainers tubes or equivalent (1 x 7 mL tube),
- For bismuth whole blood concentration determination: coded sodium citrate-coated Vacutainer tubes or equivalent (1 x 7 mL tube).
- For TMB whole-blood concentration determination: coded sodium citrate-coated Vacutainer tubes or equivalent (2 x 7 mL tubes).

3) Processing

Processing of one (1) blood sample per patient for bismuth plasma concentration determination:

Following collection, each 7 mL EDTA tube will be centrifuged at 4°C and 1500 g for 10 minutes; the resulting plasma will be extracted and divided into even numbers of opaque polypropylene snap-cap tubes (minimum two tubes) and frozen at a minimum of -20°C until shipment to the central laboratory for analysis of bismuth plasma concentrations.

Processing of one (1) blood sample per patient for bismuth whole blood concentration determination:

The 1 x 7 mL sample will be drawn on citrate-coated tubes not centrifuged, protected from light and frozen at -20°C before transport for whole blood measurement of bismuth.

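### The count of subjects needing more than 24 h to fall to 50 µg/L omits slow recoverers sampled more than 24 h after their last dose

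*Protocol*

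**What the plan says.** Section 11.7.7 uses each Day 11 result in two ways.

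- For every subject it estimates a time-corrected level, C_min, by dividing the observed value by exp(−0.0347·t), "where t is the time elapsed between last dose intake and sampling time". The rate constant comes from an assumed half-life of 19.95 h.
- It then sets that estimate aside for the threshold: "Individual observed results will also be classified as" above or below 50 µg/L. Those under the cut-off need nothing further under the plan, and the conclusion drawn about them uses neither t nor C_min: "such subjects will be considered to have reached safe whole-blood levels within an acceptable time".

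The recovery time T_recov = ln(50/C_min)/(−0.0347) is described only for subjects above 50 µg/L. The section closes by saying that the number needing more than 24 h, and the time they need, will inform the conclusion on bismuth toxicity.

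On timing, Appendix 2 places the second draw "the day after the end of treatment with Pylera® plus PPI (EOT Visit"), with no window in hours. Section 9.1.2 says that once the Day 0 sample is taken "subjects will be given an appointment for the second blood sampling (D11 sample) and subjects may initiate treatment with Pylera". Section 11.5.1 records the time since last intake at each draw. Section 1.1 ties the threshold to duration, speaking of "sustained steady-state blood levels of bismuth lower than 50" µg/L.

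**The concern.** The criterion is a recovery time measured from the last dose, but the filter that decides who gets a recovery time is a concentration measured at an unspecified number of hours after that dose. The two agree only if the sample is early enough. When it is late, a subject can be below 50 µg/L at the draw and still have needed more than 24 h to get there. That subject is classed as recovered in an acceptable time and never enters the count. Omitting such subjects can only lower the count, and the count feeds a safety conclusion.

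A second effect applies at any t. The fixed cut-off on the observed value corresponds to a different estimated last-dose level for each sampling time, so two subjects with the same exposure can be classified differently because of their appointment times.

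**Working it through.** **Inputs.** Half-life 19.95 h, k = 0.0347 per h, threshold 50 µg/L and the 24 h criterion, all from section 11.7.7. Four-times-daily dosing for 10 days with the last daily dose at bedtime, from the synopsis (Study Procedures).

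**The plan's own constant.** ln 2 / 19.95 = 0.03474, which rounds to the stated 0.0347.

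**Recovery time in terms of the observed value.** Put C_min = C_observed·exp(0.0347·t) into the recovery equation:

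T_recov = ln(C_min/50)/0.0347 = t + ln(C_observed/50)/0.0347.

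If C_observed is below 50 the logarithm is negative, so T_recov < t.

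- **t of 24 h or less:** T_recov is below 24 h for everyone observed below 50. The plan's wording follows and nobody is miscounted.
- **t above 24 h:** T_recov exceeds 24 h whenever C_observed > 50·exp(−0.0347·(t − 24)).

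| t (h) | Observed values below 50 µg/L with T_recov > 24 h |
|---|---|
| up to 24 | none |
| 30 | 40.6 to 50 |
| 36 | 33.0 to 50 |
| 48 | 21.7 to 50 |

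Example: 40 µg/L at 36 h gives C_min = 40·exp(0.0347·36) = 139.5 µg/L and T_recov = 36 + ln(0.8)/0.0347 = 29.6 h, yet the subject is passed. Equivalently, T_recov > 24 h means C_min above 50·exp(0.0347·24) = 115 µg/L, whatever t is.

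**Can t exceed 24 h?** The clock times here are assumptions. Ten days of four doses is 40 doses, and the Day 11 draw is taken at 08:00 to 18:00.

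- First dose on the morning of Day 1, last dose about 22:00 on Day 10: t = 10 to 20 h.
- First dose with the evening meal on Day 0 (2 doses that day, 36 on Days 1 to 9, 2 on Day 10), last dose about noon on Day 10: t = 20 to 30 h.
- First dose at midday on Day 0 (3 + 36 + 1), last dose about 08:00 on Day 10: t = 24 to 34 h.

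Missed final doses lengthen t further. Section 1.2 names poor compliance and misuse among the conditions the study is meant to observe.

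**Meaning of the cut-off at other times.** An observed 50 µg/L back-extrapolates to 50·exp(0.0347·t): 71 µg/L at 10 h, 100 at 20 h, 115 at 24 h and 174 at 36 h.

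**The case against.** The strongest reply is that the plan tests recovery time, not level at last dose, and that for a sample taken on schedule its rule is exactly right. That stands: with a bedtime last dose and a daytime draw on Day 11, t is about 10 to 20 h and no subject is miscounted. The 36 h and 48 h cases need missed doses, an earlier last dose or a late visit.

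Departures from schedule are also not ignored. Section 7.7 requires them to be documented, section 11.6 lists a significant visit-window change as a deviation, and section 11.7.1.2 excludes major deviations from the Per Protocol population. But no window in hours is stated against which to judge a sample, and a course begun on Day 0 can give t above 24 h with no deviation at all. Documenting a deviation does not put the subject into the count.

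Classifying on the measured value is defensible too. C_min is "grossly estimated assuming an elimination half-life of 19.95 hours", one value for everyone, although section 1.1 describes rapid distribution after dosing. This is a reason to keep the observed classification, not to omit the other, since the plan already relies on C_min for T_recov.

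A reader might go further and infer that end-of-treatment levels above the alert value, or even the 100 µg/L panic value, are routinely passed as safe. The documents do not support that. Both values are defined in section 1.1 for sustained concentrations, and a one-instant extrapolation does not show a sustained breach. The same section reports transient values above 50 and 100 µg/L and sees no evidence that such peaks are toxic. An estimate above 100 also needs t above about 20 h. Nor does mistimed sampling always favour the product: a subject who starts late against an appointment already fixed could be sampled while still on treatment.

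**Conclusion.** The point holds in a limited form. Up to 24 h after the last dose the rule agrees with the plan's own criterion. Beyond 24 h it leaves out subjects whose estimated recovery time exceeds 24 h, over a band that widens with t (9.4 µg/L wide at 30 h, 17.0 at 36 h). The protocol allows such timing. At shorter t the effect is one of interpretation: the observed cut-off stands for a last-dose estimate that depends on appointment time.

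The size rests on the plan's single half-life and mono-exponential decline. How many subjects fall in the affected band cannot be derived from the protocol. Phase I results in section 1.1 (no sustained level above about 20 µg/L; transient blood values above 100 µg/L in 1 of 28 subjects) suggest few, since an omitted subject needs an estimated last-dose level above 115 µg/L. Referral of symptomatic subjects regardless of level (section 3.2) limits the clinical consequence but does not repair the count. This should be fixed; it is not critical.

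**What to change.** In section 11.7.7:

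1. Compute T_recov from C_min for all subjects and count T_recov > 24 h over all of them. A C_min of 50 µg/L or less gives a T_recov of zero or below and simply counts as recovered.
2. Report above/below 50 µg/L for both the observed value and C_min.
3. Confine the analysis conclusion of recovery within an acceptable time to subjects whose T_recov is 24 h or less. The same passage also carries the no-further-action and referral wording; the sponsor must reconcile these with the revised analysis statement.

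In section 9.2.1 and Appendix 2, state the intended sampling interval in hours after the actual last dose, and list samples that fall outside it.

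The cost is some wording and one derived variable, because last-dose and sampling times are already collected. The count may come out slightly less favourable, and it will lean for more subjects on an assumed half-life that the plan already uses.
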